## 8.8 Clinical Laboratory Evaluations

See Appendix B for the list of clinical laboratory tests to be performed and to the Schedule of Procedures in Appendix A for the timing and frequency. See the Central Laboratory Manual for detailed sample collection, handling, storage, and shipping instructions.

The Investigator must review the laboratory report, document this review, and record any clinically relevant changes occurring during the study in the adverse event section of the eCRF. The laboratory reports must be filed with the source documents. Clinically significant abnormal laboratory findings are those which are not associated with the underlying disease, unless judged by the Investigator to be more severe than expected for the patient's condition.

All laboratory tests with values considered clinically significantly abnormal during participation in the study should be repeated until the values return to normal or Baseline or are no longer considered clinically significant by the Investigator or Medical Monitor.

- If such values do not return to normal/Baseline within a period of time judged reasonable by the Investigator, the etiology should be identified, and the Sponsor notified.
- All protocol required laboratory assessments, as defined in Appendix B, must be conducted in accordance with the Central Laboratory Manual and the Schedule of Procedures.
- If laboratory values from non-protocol specified laboratory assessments performed at the site's local laboratory require a change in patient management or are considered clinically significant by the Investigator (e.g., SAE or adverse event), then the results must be recorded in the eCRF.

## 8.9 Vital Signs

Vital signs will be measured as indicated in Appendix A. The following measurements will be obtained: sitting blood pressure, heart rate, respiratory rate, and oral temperature.

- Temperature, blood pressure, respiratory rate, and heart rate measurements will be assessed in a seated position. Blood pressure will be measured with a completely automated device. Manual techniques will be used only if an automated device is not available.
- Blood pressure, heart rate, and respiratory rate measurements should be preceded by at least 5 minutes of rest for the patient in a quiet setting without distractions (e.g., television or cell phones).
- Vital signs (to be taken before blood collection for laboratory tests) will consist of 1 heart rate and 1 blood pressure measurement and recorded on the eCRF.

## 8.10 Height, Weight, and Body Mass Index Determination

Height and weight will be assessed as indicated in Appendix A.

- Height will be recorded in centimeters. Weight will be recorded in kilograms. Body mass index will be calculated using the following formula:
  - Kilograms and centimeters.
    - With the metric system, the formula for BMI is weight in kilograms divided by height in meters squared. Since height is commonly measured in centimeters, divide height in centimeters by 100 to obtain height in meters.

### **8.11 Physical Examinations**

A complete physical examination will be performed as indicated in Appendix A. A physical examination will be performed at the Screening Visit and Week 24.

The physical exam will assess the following body systems:

- General appearance
- Skin
- Lymphatics
- Head, ears, eyes, nose, and throat
- Cardiovascular
- Respiratory
- Abdominal
- Musculoskeletal
- Neurological

Any clinically significant findings must be documented in the source and added to the medical history if found at the Screening Visit or recorded as an adverse event if new or worsened from Baseline at one of the post-Baseline visits.

### **8.12 Electrocardiograms**

A single 12-lead ECG will be obtained as indicated in Appendix A using an ECG machine that automatically calculates the heart rate and measures PR, QRS, QT, and QTc intervals. Results will be recorded in the eCRF.

### **8.13 Index Shoulder Assessment**

The index shoulder assessment will be performed by the blinded assessor at the days indicated in Appendix A. The index shoulder will be assessed for tenderness, heat/redness, swelling, and effusion. The index shoulder assessment will also include a measurement of active and passive ROM. Ranges of motion will be measured with a goniometer and include glenohumeral joint flexion, glenohumeral joint abduction, glenohumeral external rotation, and glenohumeral internal rotation in 45° or comfort abduction as defined in Appendix D. Ranges of motion assessments will be performed bilaterally (on the index and contralateral shoulder) at the Screening Visit.

### **8.14 Placebo Response Reduction and Accurate Pain Reporting Trainings**

#### **8.14.1 Placebo Response Reduction Training**

The PRR training consists of a set of patient and staff educational materials for training on appropriate expectations of personal benefit while participating in a clinical trial. The purpose is to provide patients truthful information that will neutralize the typically excessive expectations that drive high placebo responses in clinical studies. Patients will receive training as indicated in Appendix A. The training video is approximately 10 minutes and must be completed prior to any patient questionnaires.

#### 8.14.2 Accurate Pain Reporting Training

The APR training consists of a set of patient and staff educational materials and instructions on how to accurately and reliably report pain scores and on the proper use of pain intensity scales, with the aim of increasing patients' pain reporting accuracy. Patients will receive training as indicated in Appendix A. The training video is approximately 10 minutes and must be completed prior to any patient questionnaires.

## **9 STATISTICS**

A comprehensive Statistical Analysis Plan (SAP) will be written and approved prior to database lock for this study. Each shoulder condition will be analyzed completely separately. In general, the same analysis methods will be used for both shoulder conditions, and any differences in analyses between the shoulder conditions will be detailed in the SAP.

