## 5 STUDY TREATMENTS

### 5.1 Treatment Groups

Eligible patients with glenohumeral OA or shoulder AC will be randomized in a 1:1 ratio within their shoulder condition (OA or AC) and treated in the following arms:

- Nominal 32 mg FX006 as a 5 mL IA injection to the index shoulder
- Placebo (sterile normal saline) as a 5 mL IA injection to the index shoulder

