## 9.3 Analysis Populations

For each shoulder condition, the following populations are planned for this study:

- Full Analysis Set (FAS) Population: All patients who receive a complete dose of study medication and have Baseline and at least 1 post-dose efficacy endpoint assessment. The FAS Population will be used to examine efficacy for both the primary and secondary endpoints.
- Safety Population: All patients who receive at least 1 dose of study medication. The Safety Population will be used to assess safety and tolerability.
- Per Protocol Population: All patients in the FAS Population who complete the Week 24 visit with no major protocol deviations that may impact the evaluation of the primary efficacy endpoint based on blinded data prior to database lock.

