#### 9.4.2 Analysis of Safety

##### 9.4.2.1 Analysis of adverse events

Safety analyses will be performed on the Safety Population. Adverse events will be coded using the Medical Dictionary for Regulatory Activities (MedDRA). Incidences (number and percent) of treatment-emergent adverse events (TEAEs), those events that start after dosing or worsened in severity after dosing, will be presented by treatment. Incidences of TEAEs will also be presented by maximum severity and relationship to study medication.

Similar presentations will be provided for SAEs, adverse events leading to withdrawal from the study, or adverse events leading to death. Analysis of adverse event data will include examination of the incidence rates of index shoulder-related TEAEs.

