#### 9.4.6 Sample Size Determination

Approximately 250 patients will be randomized in a 1:1 ratio to either FX006 or placebo (approximately 136 patients with glenohumeral OA and approximately 114 patients with shoulder AC). Sample sizes were estimated to yield a statistically significant difference ( $\alpha = 0.05$ , 2-sided) between the FX006 and placebo groups in the average daily shoulder pain with movement score at Week 12 (the first secondary endpoint for each shoulder condition). For glenohumeral OA, the true difference between the groups was assumed to be 1, with a standard deviation of 2, based on data observed in knee OA studies of FX006 and taking into consideration the clinical significance of a 1-point difference between the treatment groups. For shoulder AC, the true difference between the groups was assumed to be 1.2, with a standard deviation of 2.1, based on a review of the existing literature. The primary endpoint analyzing the AUC for the weekly mean of the average daily shoulder pain with movement score over 8 weeks should, therefore, have >80% power to show a significant difference between the FX006 and placebo groups. As the 2 shoulder conditions (glenohumeral OA and shoulder AC) are combined into 1 protocol strictly for ease of administration, all statistical testing will be performed separately for each shoulder condition and the overall type I error rate will be controlled at the  $\alpha = 0.05$  level within each shoulder condition.

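### Safety is planned per shoulder condition only, with no prespecified combined summary, although both cohorts receive the same injection and follow-up

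*Combined protocol and SAP*

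**What the plan says.** The Synopsis (Statistical Analyses) and Section 9 state the same rule: "Each shoulder condition will be analyzed completely separately". Neither confines it to efficacy. Section 9.3 opens its list of analysis sets with "For each shoulder condition, the following populations are planned for this study", and the Safety Population is on that list. The same section adds: "The Safety Population will be used to assess safety and tolerability". Section 9.4.2.1 follows with "Safety analyses will be performed on the Safety Population", presents incidences by treatment, and singles out the treated joint: "Analysis of adverse event data will include examination of the incidence rates of index shoulder-related TEAEs". Section 9.4.2.2 plans descriptive statistics for laboratory data and vital signs. No safety test, interval or detectable rate is given.

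The reason for separation is in the Synopsis (Sample Size Determination) and Section 9.4.6. The two conditions are "combined into 1 protocol strictly for ease of administration, all statistical testing will be performed separately for each shoulder condition", with type I error controlled within each condition. Nothing there refers to safety.

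On exposure, Sections 3.1 and 5.1 give both conditions the same single 5 mL injection of 32 mg FX006 or saline, randomized 1:1 within condition and followed for 24 weeks. The Synopsis places the injection in the glenohumeral joint under ultrasound guidance for all patients. Table 1 applies one visit schedule, and Section 8.1 one set of adverse event rules.

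**The concern.** Assessing safety is a secondary objective (Section 2.2). The earlier safety experience summarised in Section 1.3.4 comes under the heading of knee OA; for the shoulder, Section 1.3.1 reports only plasma pharmacokinetics. This trial is thus the main source in the document for how the shoulder tolerates the injection.

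Separate testing protects the error rate of two efficacy claims. Descriptive safety tables make no such claim, so the argument does not carry over. Reactions in the injected joint and systemic steroid effects arise from the same product, dose, volume and joint in both cohorts. If the plan stops at per-condition tables, each statement about an uncommon event rests on about 57 or 68 FX006 patients, when a comparison that still respects the randomization could use about 125.

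**Working it through.** **Inputs.** Section 9.4.6 plans "approximately 136 patients with glenohumeral OA and approximately 114 patients with shoulder AC". With 1:1 allocation (Section 5.1), FX006 patients number 136/2 = 68 (OA) and 114/2 = 57 (AC), or 125 in all. Section 9.4.3 caps each condition at 150. The documents give no adverse event rates, so every rate below is an assumption. All randomized patients are assumed to be dosed.

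**The plan's own figure.** The only design figure is efficacy power above 80%. For two means with n per arm, power = Φ(δ / (σ√(2/n)) − 1.96).

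- OA, δ = 1, σ = 2, n = 68: Φ(2.92 − 1.96) = 83.0%.
- AC, δ = 1.2, σ = 2.1, n = 57: Φ(3.05 − 1.96) = 86.2%.

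Both agree with the plan, which confirms the arm sizes. There is no safety figure to reproduce.

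**Zero-event bound.** If no case is seen among n patients, the exact one-sided 95% upper limit for the true rate is 1 − 0.05^(1/n).

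**Risk-difference precision.** With rate p in both arms, the 95% half-width is 1.96 × √(2p(1 − p)/n). If the rate is the same in both conditions, weighting the two within-condition differences by sample size gives variance (68/125)² × 2p(1 − p)/68 + (57/125)² × 2p(1 − p)/57 = 2p(1 − p)/125. The combined column therefore also describes the stratified estimate.

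**Chance of at least one FX006 case.** 1 − (1 − p)^n.

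| Quantity | OA (68) | AC (57) | Combined (125) |
|---|---|---|---|
| Zero-event upper bound | 4.3% | 5.1% | 2.4% |
| Half-width, p = 5% | 7.3 points | 8.0 points | 5.4 points |
| Half-width, p = 10% | 10.1 points | 11.0 points | 7.4 points |
| At least one case, p = 1% | 49.5% | 43.6% | 71.5% |
| At least one case, p = 2% | 74.7% | 68.4% | 92.0% |

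**Reading the table.** The per-condition bounds are 1.8 and 2.2 times the combined bound. Combining narrows the risk-difference interval by 1 − √(68/125) = 26% relative to OA and 1 − √(57/125) = 32% relative to AC. The last two rows compare one cohort read alone with the whole trial. The chance that a case appears in at least one cohort is 1 − 0.99^68 × 0.99^57 = 71.5% at a 1% rate, exactly the combined figure, so separate tables do not change it.

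**At the cap.** With 150 per condition (75 FX006 patients each), the bound is 3.9% per condition against 2.0% for 150 combined. The gap persists.

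**Limit of the approximation.** The half-widths are Wald intervals. At 5% the expected counts per arm are 3.4 (OA), 2.85 (AC) and 6.25 (combined), so they indicate relative size only.

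**The case against.** The best reply has four parts.

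*Nothing is lost.* Every adverse event in both cohorts is collected and reported by treatment, and anyone can add two tables of counts. This stands. A reader might infer that separate analysis throws away about half the trial's ability to detect harm. The documents do not support that: the chance of seeing an event somewhere in the trial is the same, and a factor of about two fits only the zero-event bound. What adding counts afterwards does not supply is a planned, stratified comparison; Section 9.4.4 requires post-hoc analyses to be labelled as such.

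*The SAP may provide it.* Section 9 says a SAP will be approved before database lock, and Section 9.4.2.1 does not itself mention condition. That is fair, and one cannot say that no combined table will ever be produced. But the stated rule points the other way, and Section 9 leaves to the SAP only differences in analysis between the conditions.

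*The cohorts differ.* AC has a different pathogenesis and is more common in patients with diabetes (Section 1.1). AC patients follow the home exercise program, and the surgery exclusions differ (Section 4.2, criteria 9 and 10). This stands as a reason to stratify and to keep the per-condition tables. A crude pooled rate describes a mixture of 54% OA and 46% AC set by the sample sizes, and is not the rate for either indication. Both AC arms do the exercises, so the within-condition comparison remains fair.

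*Safety is not tested, so prespecification protects no error rate.* True. Its value here is that the main safety summaries are chosen before the data are seen.

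**Conclusion.** The point holds as a gap in precision and prespecification. The complete-separation rule reaches safety without a stated reason, and no combined summary is planned despite the shared exposure. Against a combined analysis, the zero-event bound is 4.3% (OA) and 5.1% (AC) instead of 2.4%. The risk-difference half-width at an assumed 5% rate is 7.3 and 8.0 points instead of 5.4. The zero-event bounds depend only on the arm sizes; the half-widths also depend on the assumed rate and, for the combined figure, on a similar rate in both conditions. Efficacy testing and type I error control are unaffected. This is a worthwhile, inexpensive improvement and not a flaw that threatens the trial's conclusions.

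**What to change.** - **Synopsis and Section 9:** limit the complete-separation rule to efficacy.
- **Section 9.3:** keep the per-condition Safety Populations and add an overall one, the union of the two.
- **Section 9.4.2:** prespecify pooled tables by treatment for TEAEs, SAEs and index-shoulder-related TEAEs. Add the FX006-minus-placebo risk difference stratified by shoulder condition, with a confidence interval suited to sparse counts, such as a stratified Miettinen–Nurminen score interval. Show these beside the per-condition tables, which stay primary for each indication.

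The cost is wording and a few tables, with no new data or patients. There are two drawbacks. Section 9.4.4 speaks of database lock for each shoulder condition; if the locks fall at different times, the pooled tables must wait for the later one. The pooled rate also describes an OA/AC mixture, so the SAP should say that it is to be read with the per-condition results.

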### **9.1 General Considerations and Methods**

Data collected in this study will be presented using summary tables, figures, and patient data listings. Summary tables will present data by treatment group and, if applicable, by time of collection. Continuous variables will be summarized using descriptive statistics, specifically the mean, median, standard deviation, minimum, and maximum. Categorical variables will be summarized by frequencies and percentages. Figures will be used to support the presentation of certain data. Sensitivity analyses may be performed to examine the effect of missing data, as well as the effect of Baseline imbalance, should it occur.

All confidence intervals (CIs), statistical tests, and resulting p-values will be reported as 2-sided. Multiplicity will be addressed by analyzing the key secondary endpoints sequentially in the order presented in the protocol, testing each endpoint at the nominal  $\alpha = 0.05$ , 2-sided level to ensure overall type I error control at the 2-sided 0.05 level.

#### **9.1.1 Demographics and Baseline Characteristics**

Demographic and Baseline characteristics will be listed by study site and patient and will be summarized by treatment.

#### **9.1.2 Exposure**

Treatment exposure will be listed by study site and patient and will be summarized by treatment.

### **9.2 Study Data**

Study data identified in this protocol will be collected and source verified at the study sites completing the study visits. All study data will be formulated into data sets to provide transparency, traceability, and integrity of study analysis results from collection sources. Observed study data will be mapped to the Clinical Data Interchange Standards Consortium (CDISC) Study Data Tabulation Model (SDTM) and serve as the source data from the study. All study analyses will be completed using analysis data sets that are derived from the SDTM and follow the CDISC Analysis Data Model (ADaM) architecture.

#### **9.2.1 Clinical Data – Clinical Data Interchange Standards Consortium Study Data Tabulation Model**

Clinical data will be mapped to CDISC SDTM using implementation guide version 3.2. No derived data required for analyses will be included in the SDTM domains. All SDTM domains will be fully documented with define documents (DEFINE.XML) and a Study Data Reviewer's Guide after database lock and final analyses are completed.

## 9.2.2 Analysis Data – Clinical Data Interchange Standards Consortium Analysis Data Model

All planned and exploratory analyses will be completed using CDISC compliant ADaM data sets derived from the SDTM domains for this study. Analysis data sets will contain all derived study endpoints required for analysis. All ADaM analysis data sets will be fully documented with define documents (DEFINE.XML) and an Analysis Data Reviewer’s Guide after database lock and final analyses are completed.

## 9.3 Analysis Populations

For each shoulder condition, the following populations are planned for this study:

- Full Analysis Set (FAS) Population: All patients who receive a complete dose of study medication and have Baseline and at least 1 post-dose efficacy endpoint assessment. The FAS Population will be used to examine efficacy for both the primary and secondary endpoints.
- Safety Population: All patients who receive at least 1 dose of study medication. The Safety Population will be used to assess safety and tolerability.
- Per Protocol Population: All patients in the FAS Population who complete the Week 24 visit with no major protocol deviations that may impact the evaluation of the primary efficacy endpoint based on blinded data prior to database lock.

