#### **STATISTICAL ANALYSES:**

Data collected in this study will be presented using summary tables, figures, and patient data listings. Summary tables will present data by treatment group and, if applicable, by time of collection. Continuous variables will be summarized using descriptive statistics, specifically the mean, median, standard deviation, minimum, and maximum. Categorical variables will be summarized by frequencies and percentages. Figures will be used to support the presentation of certain data. Sensitivity analyses may be performed to examine the effect of missing data, as well as the effect of Baseline imbalance, should it occur.

All confidence intervals, statistical tests, and resulting p-values will be reported as 2-sided. Multiplicity will be addressed by analyzing the key secondary endpoints sequentially in the order presented in the protocol, testing each endpoint at the nominal  $\alpha = 0.05$ , 2-sided level to ensure

---

---

overall type I error control at the 2-sided 0.05 level. Each shoulder condition will be analyzed completely separately. In general, the same analysis methods will be used for both shoulder conditions.

For each shoulder condition, the following populations are planned for this study:

- Full Analysis Set (FAS) Population: All patients who receive a complete dose of study medication and have Baseline and at least 1 post-dose efficacy endpoint assessment. The FAS Population will be used to examine efficacy for both the primary and secondary endpoints.
- Safety Population: All patients who receive at least 1 dose of study medication. The Safety Population will be used to assess safety and tolerability.
- Per Protocol Population: All patients in the FAS Population who complete the Week 24 visit with no major protocol deviations that may impact the evaluation of the primary efficacy endpoint based on blinded data prior to database lock.

All study analyses will be completed using analysis data sets that are derived from the Study Data Tabulation Model and follow the Clinical Data Interchange Standards Consortium Analysis Data Model architecture.

Covariates for efficacy analyses will include Baseline average daily shoulder pain with movement score, Baseline score for the endpoint, analysis site, and, for AC patients, pain duration since onset. Other covariates may also be explored.

---

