### 5.3 Randomization and Blinding

Patients from each shoulder condition will be randomized on Day 1 to 1 of 2 treatment arms (FX006 or placebo) using centralized randomization accessed through an interactive voice/web response system randomization (IxRS) module.

Glenohumeral OA patients will be stratified by the Baseline average daily shoulder pain with movement score (0 to 10 NRS) (5.0 to <7.0 or ≥7.0 to 9.0). Shoulder AC patients will be stratified by the Baseline average daily shoulder pain with movement score (0 to 10 NRS) (5.0 to <7.0 or ≥7.0 to 9.0) and pain duration since onset at Screening (1 to 3 months, inclusive, or >3 to ≤6 months).

The blinded-assessor technique will be used in this study to maintain double-blind conditions. Key study site staff roles are defined below and a site-specific blinding plan will be developed to ensure the blind is maintained throughout the duration of the study. Treatments will be prepared by an unblinded pharmacist/coordinator who has experience with the preparation of study medication and who has been properly trained by the Sponsor or designee. Intra-articular injections will be performed by an unblinded injector.

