### 5.5.3 Study Medication Administration

Only patients enrolled in the study may receive study medication and only authorized site staff may supply or administer study medication.

Any difficulties with the study medication administration should not be reported to the blinded assessor unless it is a direct cause of an adverse event. In the event of difficulties during the procedure with administering the study medication, please proceed as follows:

- Stop the procedure.
- Do not attempt to reinject.
- Report the event to the unblinded coordinators at the site and to the unblinded team at Flexion Therapeutics, Inc. via the Product Complaint Form.
- The patient and blinded study personnel (coordinators and Investigators) should not be informed the procedure was stopped.

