#### 5.5.4 Treatment Compliance

Study medication will be administered by the unblinded injector in the clinic. Details regarding study medication administration will be documented in the eCRF. The receipt, dispensation, and return/destruction of any study medication will be properly documented.

If for any reason the administration of study medication is stopped before the entire volume is injected, the injector should document the reason for stopping administration.

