#### **6.4 Treatment Visit (Day 1)**

The following procedures will be performed at the Treatment Visit (Day 1):

- Confirm eligibility based on Inclusion and Exclusion Criteria (see Sections 4.1 and 4.2, respectively) prior to administration of study medication.
  - Review the average daily shoulder pain with movement (0 to 10 NRS) to ensure at least 5 out of the 7 days prior to Day 1 have been recorded.
- Complete APR and PRR trainings prior to patient questionnaires and administration of study medication.
- Administer the EQ-5D-5L, SPADI, and ASES after completion of APR and PRR training, but prior to any other assessments.
- Review and update medical history prior to administration of study medication.

- Review and update prior treatments and medications prior to administration of study medication.
- Review SI question and rescue medication usage in the eDiary.
- Perform index shoulder assessment including active and passive ROM prior to administration of study medication.
- Obtain vital signs prior to administration of study medication.
- Perform urine pregnancy test prior to administration of study medication (for women of childbearing potential).
- Perform randomization prior to administration of study medication.
- Perform index shoulder aspiration prior to administration of study medication.
- Administer study medication following standard of care procedure.
- Dispense/return rescue medication as needed.
- Assess adverse events and concomitant medications (post injection).
- For shoulder AC patients only, a Home Exercise Program (HEP) will be implemented 3 days following injection and performed twice daily (see Appendix C).

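### The Full Analysis Set drops randomised patients whose injection was stopped part-way, and no required efficacy analysis puts them back

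*Combined protocol and SAP*

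**What the plan says.** Section 9.3 defines the FAS as "All patients who receive a complete dose of study medication and have Baseline and at least 1 post-dose efficacy endpoint assessment". The Synopsis has the same definition and adds: "The FAS Population will be used to examine efficacy for both the primary and secondary endpoints".

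The other two sets do not bring back a patient with an incomplete injection. Per Protocol is "All patients in the FAS Population who complete the Week 24 visit with no major protocol deviations", so it lies inside the FAS. The Safety Population is used for safety only.

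The order of events on Day 1 is set in section 6.4: "Perform randomization prior to administration of study medication". Section 5.3 adds: "Intra-articular injections will be performed by an unblinded injector". Section 5.5.3 tells the injector to stop if there is difficulty, and then: "Do not attempt to reinject". It continues: "The patient and blinded study personnel (coordinators and Investigators) should not be informed the procedure was stopped". Section 5.5.4 foresees the same event: "If for any reason the administration of study medication is stopped before the entire volume is injected, the injector should document the reason".

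Section 9.1 allows, but does not require, sensitivity analyses for missing data and Baseline imbalance. Section 9 leaves further detail to an SAP that is still to be written. No separate SAP text is in the document reviewed here.

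**The concern.** The plan foresees patients who are randomised and partly injected, and who need not know that the procedure was stopped. It then removes them from every efficacy set. The removal turns on an event after randomisation that arises while someone who knows the allocation is holding the syringe. FX006 is a suspension that has to be resuspended, and placebo is saline, so unequal stopping is conceivable.

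Two different things are at stake:

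- **Target.** If a partial FX006 injection gives less benefit, the FAS shows a larger effect than the one in all patients whose injection was started. This alone does not raise type I error.
- **Selection.** If the two arms lose different numbers of patients, or different kinds of patient, those who remain are no longer comparable. This can push the result either way, even when the drug does nothing.

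**Working it through.** **Inputs from section 9.4.6.** Two-sided alpha 0.05, 1:1 allocation. OA: 136 patients (68 per arm), difference 1, SD 2. AC: 114 patients (57 per arm), difference 1.2, SD 2.1. These describe the Week 12 score; no separate difference is given for the 8-week AUC, so the Week 12 values are used throughout.

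**The plan's own figure.** SE = SD × √(2/n per arm).

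- OA: 2 × √(2/68) = 0.343. Power by noncentral t is 82.5%.
- AC: 2.1 × √(2/57) = 0.393. Power is 85.6%.

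Both agree with the stated power above 80%.

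**General formula.** In each arm let q be the share of injections stopped, and g the amount by which stopped patients improve less than completed ones. The mean over all injected patients is the completers' mean minus q × g. Hence

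FAS difference − all-injected difference = qF·gF − qP·gP (F = FX006, P = placebo).

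The documents give none of these four quantities. All values below are assumptions.

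**Change of target.** Suppose stopped patients have ordinary prognosis and the only loss is drug benefit. Then gP = 0, and the shift is f × lost benefit, where f is the stop rate in the FX006 arm. With the whole assumed benefit lost:

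| f | OA shift (share of SE) | AC shift (share of SE) |
|---|---|---|
| 1% | 0.01 (3%) | 0.01 (3%) |
| 3% | 0.03 (9%) | 0.04 (9%) |
| 5% | 0.05 (15%) | 0.06 (15%) |
| 10% | 0.10 (29%) | 0.12 (31%) |

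If half the benefit is kept, the shifts halve. In OA, 3% is about 2 of 68 patients and 10% about 7.

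**Selection with no drug effect.** Here the shift is pure bias.

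- Stops in one arm only, at 1% to 3%, with a 2-point gap: 0.01 × 2 = 0.02 up to 0.03 × 2 = 0.06 points. Type I error by noncentral t (noncentrality = bias/SE) is 5.0% to 5.3% in both conditions.
- Rates 5 percentage points apart, with a 2-point gap in both arms: 0.05 × 2 = 0.10 points. Type I error is 6.0% (OA) or 5.7% (AC).
- Equal rates of 5%, but a 2-point gap in FX006 and none in placebo: 0.05 × 2 − 0.05 × 0 = 0.10 points again. Equal stop rates are therefore no guarantee.
- Equal rates and equal gaps: 0.

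Reversing the sign of the gap reverses the direction of the bias.

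**Power if these patients were kept in the primary analysis.** Assume that they gain nothing, so that the difference becomes (1 − f) × the planned one, with n and SD fixed:

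| f | OA, kept | AC, kept | OA, excluded as now |
|---|---|---|---|
| 0 | 82.5% | 85.6% | 82.5% |
| 3% | 80.2% | 83.5% | 81.3% to 81.9% |
| 5% | 78.5% | 81.9% | 80.5% to 81.5% |
| 10% | 74.1% | 77.7% | 78.3% to 80.4% |

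The last column shows that exclusion costs power too; the lower value applies if placebo injections are stopped equally often. The net OA loss from keeping the patients is about 1 to 2, 2 to 3, or 4 to 6 percentage points.

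**The case against.** **Every size is assumed.** This stands. A bias of 0.10 points needs stopping that is fairly common and closely tied to outcome. Nothing in the documents shows this, and a Phase 2 injection trial may see only one or two stops per arm.

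**The mechanism is conjecture, and there are safeguards.** Largely right. Section 5.3 keeps the unblinded team away from the patient apart from possible consent duties, and section 8.13 gives the index shoulder assessment to a blinded assessor. Section 5.5.3 ties stopping to difficulty with the procedure. No text says that resuspension leads to more stops or that stopped patients have a different prognosis. These safeguards protect the outcome assessment, however; they do not affect who enters the FAS.

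**The SAP can supply the analysis.** It can. The defect is that the protocol does not require it. The choice should be fixed before stop rates by arm are known.

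**A completed-injection target is legitimate.** A sponsor may prefer it. A reader might then take the FAS to estimate exactly the effect of a complete injection. The documents do not support that, because completers in the two arms are comparable only if stopping is unrelated to arm and prognosis.

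**Data will be thin.** Partly right. Section 4.3 lists injection-related technical problems among the withdrawal reasons. For withdrawn patients it provides for safety follow-up and attempted end-of-study assessments, not for continued diary entries.

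**Conclusion.** The point holds as a minor one. The set that carries the primary and secondary endpoints excludes randomised, injected patients on an event after randomisation, and no required analysis shows what difference this makes. Under assumption the effect is negligible at 1% to 3% stops and reaches about 0.10 points only when stopping is frequent or strongly selective.

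Two stronger readings are tempting and are not supported. One is that the FAS will overstate the benefit: that follows only if partial FX006 injections work less well, and a stop near full volume may lose little. The other is that type I error is inflated: that needs a difference between arms in stop rate or in the kind of patient stopped, and the documents report neither. The calculations rest on the Week 12 planning values with a fixed SD.

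**What to change.** **Minimum.** In section 9.3 and the Synopsis, prespecify a sensitivity analysis of the primary and secondary endpoints in all randomised patients in whom the study injection was started, whatever volume was given. Require Baseline and at least one post-dose efficacy assessment, and analyse as randomised. Tabulate incomplete injections by arm from the record that section 5.5.4 already calls for. The cost is one more analysis and one table, possibly with sparse diary data for patients withdrawn for a technical problem. Primary power does not change.

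**Preferred, if the sponsor accepts the power cost.** Make that set the FAS, move the complete-dose condition to Per Protocol, and keep completers as the sensitivity analysis. If affected patients gain nothing, the smallest totals for 80% power are:

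- OA: 142 at f = 5% and 158 at f = 10%, against 136 planned.
- AC: 110 and 122, against 114 planned.

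Section 9.4.3 allows up to 150 per condition. At 150, OA power would be 82.4% (f = 5%) or 78.2% (f = 10%). That increase is tied to the SD, so it cannot be counted on.

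**Limit.** Patients never injected, and those with no post-dose efficacy assessment, stay outside either set. The change removes one post-randomisation exclusion, not all of them.
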